### 3.0 PATIENT ELIGIBILITY CRITERIA

#### 3.1 Patient Sample

Sample Size:

Group A: 18 patients

Reference Group: 15 patients

Accrual Rate:

3 patients per month

Gender:

Male and female

Age:

Patients must be at least 18 years of age.

Race/Ethnicity:

Minorities will be actively recruited. No exclusion to this study will be based on race or ethnicity.

Accrual Targets					
Ethnic Category	Sex/Gender				
	Females		Males		Total
Hispanic or Latino	2	+	2	=	4
Not Hispanic or Latino	11	+	18	=	29
Ethnic Category: Total of all subjects	13 (A1)	+	20 (B1)	=	33 (C1)
Racial Category					
American Indian or Alaskan Native	0	+	0	=	0
Asian	2	+	2	=	4
Black or African American	2	+	3	=	5
Native Hawaiian or other Pacific Islander	0	+	0	=	0
White	9	+	15	=	24
Racial Category: Total of all subjects	13 (A2)	+	20 (B2)	=	33 (C2)

(A1 = A2)

(B1 = B2)

(C1 = C2)

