### 9.5.1 Tissue Requirements for Protocol Surgery: Group A and Reference Group

Every effort should be made to collect adequate amounts of tissue.

The minimum **tissue requirements** to be collected from participants at the time of surgery include:

- 500 mg of fresh frozen tissue from the contrast enhancing portion of the tumor. This sample will be used for the determination of the primary objectives of the study for both the tumor drug distribution endpoints ([Section 9.5.5](#)) and EGFR phosphorylation endpoints ([Section 9.5.6](#))
- 100 mg of fresh frozen tissue from the non-contrast enhancing portion of the tumor (if low risk of inducing neurological injury). This sample will be used in an exploratory fashion regarding tumor drug distribution and EGFR phosphorylation.
- If sufficient tissue is available, 500 mg or more of additional enhancing tissue (for tumor sphere cultures)

The **remainder of the sample** should be fixed in formalin and processed for routine paraffin embedding and sectioning at the site, per usual site protocols in pathology.

The precise location in the tumor from which these specimens were obtained and the precise time should be recorded. Depending on local site's capabilities, if a common navigation system is used for surgical localization, segmentation of the tumor using 3D visualization software is recommended for accurate sampling localization. Using this

reconstructed model, a representative screenshot is requested demonstrating the location of the resected tissue. If not possible, then a screenshot of the MRI showing the location of the resected tissue should be included.

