### 9.5.7 Tumor Sphere Cultures

Glioma Tumor Sphere Lines will be prepared from fresh tumor samples whenever possible (i.e., if there is 500 mg or more of additional enhancing tissue) at each participating ABTC site. The consortium has successfully derived glioma tumor sphere cultures in the context of a prior clinical trial (ABTC 0906).

Whenever possible, at least 500 mg grams of viable tissue will be processed for neurosphere studies. The sterility of the specimen should be preserved while it is minced gently into 0.5 cm cubes in the operating room which optimizes conditions for cellular survival, prevents tube breakage/leakage, and maintains cells at low temperature while avoiding freezing of cells. In brief, a pre-labeled 25cc tube should be filled to the top with a low-glucose, serum-free, buffered transport medium and **placed immediately on wet ice in the operating room**. The specimen should then be inserted into a protective tube to prevent breakage, sealed in a Ziploc bag, and packed **on wet ice** in a pre-labeled styrofoam container with relevant identifying information. The starting and ending times of resection should be noted by personnel at the institution and included in the specimen identification form.

**Specimens for tumor sphere cultures must be shipped immediately from the participating ABTC site to the [name] Laboratory.** Specimens will be shipped via FedEx on the same day for delivery by 10 AM the next day (FedEx First Overnight). Seal the box and print and attach the shipping address onto the outside of the shipping container and label the container as containing biohazardous specimens. Record the shipping date, time, tracking number, and shipping information in the Batch Record.

Notification of the delivery must be made by e-mail to both [name] (email: [[contact]](mailto:[contact])) and [name] (e-mail: [[contact]](mailto:[contact])). Include the name of the courier and the tracking no. in the email.

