### **Secondary and Exploratory Objectives:**

1. All treatment or surgically related AEs will be reported descriptively. A proportion of toxicity grade  $\geq 3$  will be estimated using binomial distribution.

2. To estimate inhibition of tumor cell proliferation (KI-67), descriptive statistics will be used for summarizes results and Box plots could be used to present the difference between the treated and untreated groups.
3. To characterize ex-vivo sensitivity of tumor sphere cultures to lapatinib, the *ex-vivo* sensitivity of tumor sphere cultures established from surgical specimens to pulsatile lapatinib is defined by a minimum of 20% reduction in cell proliferation as measured by cell titer glow in the pulsatile lapatinib group compared to the untreated group. Fisher's exact test will be used for testing a difference in the proportion between the two groups.
4. To estimate tumor objective response rate as the evidence of biological activity among patients with recurrent GBM treated by lapatinib, the proportion of patients who had objective PR or CR during the course of the treatment will be estimated along with 95% confidence intervals using the exact binomial method.
5. To estimate overall survival (OS), the survival time is defined from the date of treatment start to the date of death. Patients who have not expired by the data analysis cutoff date will be censored at their last date known to be alive. The Kaplan-Meier method will be used to estimate overall survival probability and median time of survival along with a 95% confidence interval.
6. To estimate progression-free survival, The progression is defined a radiographic tumor progression, a  $\geq 25\%$  increasing from baseline scan with a confirmatory scan at least 8 weeks apart from the initial scan that tumor progression was observed. The date of progression is defined as the date of initial scan deemed tumor progression. The Kaplan-Meier method will be used to estimate progression-free survival probability and median time of survival along with a 95% confidence interval. The progression-free survival at 6-month is defined as: patient, who started treatment, is alive and progression free at the time of 6 month follow-up. The probability of 6-month progression-free survival will be estimated using binomial distribution.

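### The ex-vivo sensitivity analysis keeps only a yes/no call at an unexplained 20% cut, so the size of any group difference is never estimated

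*Combined protocol and SAP*

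**What the plan says.** Item 3 of the Secondary and Exploratory Objectives in Section 11 sets out to characterize ex-vivo sensitivity. The rule for calling a culture sensitive reads "defined by a minimum of 20% reduction in cell proliferation". The item then names its assay and comparator: "as measured by cell titer glow in the pulsatile lapatinib group compared to the untreated group". The only comparison planned is: "Fisher's exact test will be used for testing a difference in the proportion between the two groups". The item gives no significance level, expected proportions, effect size, power, estimate of the difference or confidence interval, and no section explains why 20% was chosen.

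Section 3.1 plans "Group A: 18 patients" and "Reference Group: 15 patients". Not every patient will yield a culture. Section 9.5.1 makes collection conditional: "If sufficient tissue is available, 500 mg or more of additional enhancing tissue (for tumor sphere cultures". Section 9.5.7 agrees: "Glioma Tumor Sphere Lines will be prepared from fresh tumor samples whenever possible". So 33 cultures is the planned maximum.

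Section 2.4 and Table 9.5 label the endpoint exploratory. They and Section 9.5.7 name Trypan Blue as the assay, whereas item 3 names CellTiter-Glo.

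**The concern.** Either assay gives a graded value. Once it is cut at 20%, a culture with a 21% reduction counts the same as one with 95%, and one with 19% counts the same as one with none. The plan's other thresholds, 1.5 µM and 80% inhibition, are argued for in Section 2.3; this one is not. Item 2 of the same list handles Ki-67, another exploratory two-group tumor measure, with descriptive statistics and box plots of the values.

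At stake is what the reader learns from a small set of cultures. As planned, the result is two proportions and a p-value. A non-significant p-value from so few cultures could be read as no difference, with no interval to show how large a difference remains possible. If nearly all or nearly no cultures pass 20%, the test has little left to detect.

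**Working it through.** The plan states no power, effect size or SD for this endpoint, so there is no figure to reproduce. The check asks what the cut does under two assumed readout shapes.

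**Inputs.** Group sizes 18 and 15 (Section 3.1). Two-sided 5% tests are an assumption, because item 3 states no level. The responder rates are also assumptions. The 70/25 pair borrows the target and null rates of the primary PK and PD rules, which in Section 11 apply to Group A alone; the documents do not give them as ex-vivo rates for two groups.

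**Fisher power.** Full enumeration: sum over a = 0..18 and b = 0..15 of Bin(a; 18, p1) × Bin(b; 15, p2), counting tables with two-sided p ≤ 0.05. When both groups share a rate of 20% or 50%, the true size is about 3.3–3.5%, so part of any loss is the test's own conservatism.

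**Shape 1: normal readout, pure shift.** The shift in SD units is d = Φ⁻¹(p1) − Φ⁻¹(p2):
- 70/25: 0.52 + 0.67 = 1.20
- 60/20: 0.25 + 0.84 = 1.09
- 80/50: 0.84 − 0 = 0.84

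**Shape 2: responder/non-responder mixture.** Assumed percent reduction is N(60, 12) in sensitive and N(0, 8) in insensitive cultures (mean, SD). A 20% cut separates these almost perfectly: (60 − 20)/12 = 3.3 SD below the sensitive mean and 20/8 = 2.5 SD above the insensitive mean. Fisher power is therefore essentially the same as under shape 1.

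Power at 18 v 15 (Wilcoxon and permutation figures are simulated, with an error of about 1–2 points):

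| Rates | Fisher | Wilcoxon, shift | Permutation of means, shift | Wilcoxon, mixture | Permutation of means, mixture |
|---|---|---|---|---|---|
| 70/25 | 71% | 89% | 90% | 62% | 70% |
| 60/20 | 60% | 83% | 86% | 52% | 61% |
| 80/50 | 37% | 62% | 62% | 31% | 39% |

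Under the shift, Wilcoxon gains 18, 23 and 25 points over Fisher. Under the mixture it is 9, 8 and 6 points lower in these runs; allowing for simulation error, about 6 to 11. The permutation test stays within about 3 points of Fisher under the mixture and gains 19, 26 and 25 points under the shift. At rates of 20/2 the contrast is extreme: Fisher 22%, Wilcoxon 90% under the shift but 13% under the mixture.

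**Range under shape 1.** The continuous benchmark is the t-test on the uncut values, with non-centrality d/√(1/18 + 1/15) = d/0.350 on 31 degrees of freedom. Cuts were placed midway between the group means, or so that 5% to 50% of Reference cultures pass.

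| d (SD) | t-test | Fisher, midpoint cut | Loss over all cuts (points) |
|---|---|---|---|
| 0.5 | 28% | 17% | 12–25 |
| 0.8 | 60% | 38% | 22–45 |
| 1.0 | 79% | 55% | 24–49 |
| 1.25 | 93% | 75% | 18–38 |
| 1.5 | 99% | 89% | 10–21 |
| 2.0 | 100% | 99% | 1–8 |

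Against Wilcoxon the loss is usually 1–3 points smaller. With fewer cultures and the midpoint cut, the loss against the t-test over the same six shifts is 8–27 points at 12 v 10 and 7–25 points at 9 v 8.

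**The case against.** The strongest reply is that a yes/no endpoint may suit the biology. Section 2.3 reports that lapatinib killed glioma cells with EGFR amplification or mutation and spared EGFR-wildtype cells, which suggests a split more than a smooth shift. Under such a split the working shows Fisher ahead of Wilcoxon. This stands, and it limits the point. A reader might infer that the plan throws away a flat 20 or more points of power, or that Fisher's test should be deleted. The documents support neither, because they give no readout distribution, SD or ex-vivo rates. Even under a normal shift, the loss reaches 20 points at every cut tried only for middling effects.

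Second, the endpoint is exploratory, with no power claim and no decision resting on it, and Fisher's test is valid at these counts. This also stands, and it keeps the point minor. It does not explain the 20% cut, and it does not supply the missing estimate.

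Third, a per-culture percent reduction cannot be analysed until it is defined. Item 3 words the reduction as one group against the other, so it is unclear how a single culture, especially a Reference Group one, is classed as sensitive. This is correct. It applies equally to the planned Fisher test, which also needs a call for each culture, so the definition has to come first either way.

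**Conclusion.** The point holds as one of estimation. Item 3 reduces a graded readout to yes/no at an unexplained cut, tests it one way, and never estimates how large any difference in sensitivity is, in at most 18 v 15 cultures. This needs no assumption about the data.

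The effect on power is conditional. Under a normal shift of 0.5–2.0 SD at full size, the loss from cutting and using Fisher is about 1 to 49 points against the t-test. Under a clean responder/non-responder mixture there is essentially no loss, and a rank test would do worse than Fisher. Of the tests tried, the permutation test of the mean difference is the one that holds up under both shapes. All of these figures rest on assumed rates, distributions and a two-sided 5% level. Importance is low: the endpoint is exploratory and the primary endpoints are untouched.

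**What to change.** Rewrite item 3 of Section 11 as follows.

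1. Define percent reduction for each culture as lapatinib-exposed against untreated aliquots of the same culture, in both groups. Name one assay, consistently with Sections 2.4 and 9.5.7 and Table 9.5.
2. Make that value the main analysis variable. Report the Group A minus Reference difference with a 95% CI, an exact or permutation test with its level and sidedness stated, and a plot of all values. A permutation test of the mean difference is the safer choice while the readout distribution is unknown.
3. Keep the proportion with at least 20% reduction in each group, with exact 95% CIs and Fisher's test, as a secondary summary. Give the reason for 20%, or state that it is a convention.
4. Report how many cultures were obtained in each group.

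The cost is one paragraph of text, one more analysis and a second exploratory p-value. It needs no extra patients or tissue. It needs no extra assay runs provided untreated aliquots of each culture are already part of the assay, which the documents do not state.

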## **8.0 SAFETY AND QUALITY ASSURANCE**

### **8.1 Criteria for Response Assessment**

Subjects with measurable disease will be assessed by the RANO (radiographic assessment in neuro-oncology) criteria (Wen et al. 2010). For the purposes of this study, subjects should be re-evaluated at the end of every 2 cycles (approximately every 8 weeks) with a contrast-enhanced cranial MRI scan. The response will be determined as outlined in the RANO criteria below.

The MRI obtained prior to starting post-surgery treatment cycles of lapatinib will be used as the baseline MRI for purposes of determining radiographic response.

*Measurable disease.* Bidimensionally, contrast-enhancing, measurable lesions with clearly defined margins by MRI scan, with a minimal diameter of 1 cm, and visible on 2 axial slices which are at least 5 mm apart with 0 mm skip. Measurement of tumor around a cyst or surgical cavity, if necessary, requires a minimum thickness of 3 mm. If there are too many measurable lesions to measure at each evaluation, the investigator must choose the largest two to be followed before a participant is entered on study. The remaining lesions will be considered non-measurable for the purpose of objective response determination. Unless progression is observed, objective response can only be determined when all measurable and non-measurable lesions are assessed.

Complete Response (requires all of the following):

- a) Complete disappearance of all enhancing measurable and non-measurable disease sustained for at least 4 weeks. In the absence of a confirming scan 4 weeks later, this scan will be considered only stable disease.
- b) No new lesions.
- c) All measurable and non-measurable lesions must be assessed using the same techniques as baseline.
- d) Subjects must be off corticosteroids (or on physiologic replacement doses only).
- e) Stable or improved non-enhancing (T2/FLAIR) lesions.
- f) Stable or improved clinically.

**Note:** Subjects with non-measurable disease cannot have a complete response. The best response possible is stable disease.

Partial Response (requires all of the following):

- a) Greater than or equal to 50% decrease compared to baseline in the sum of products of perpendicular diameters of all measurable enhancing lesions sustained for at least 4 weeks. In the absence of a confirming scan 4 weeks later, this scan will be considered only stable disease.
- b) No progression of non-measurable disease.
- c) No new lesions.

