## 8.2 Assessment of Response

Assessment of response will begin with the MRI performed just prior to *every odd-numbered* treatment cycle post-surgery. If during any scheduled MRI, the subject has a Complete Response or Partial Response, the MRI should be repeated prior to the next cycle. All scans are to be compared to the smallest measurement scan to date. The subject will then return to the every odd-numbered cycle schedule. This is required to confirm the duration of response. Subjects will be classified as responders if they have a minimum duration of response for 4 weeks at any time after the first post-surgery cycle of lapatinib. MRI scans of subjects showing tumor response will be centrally reviewed by a neuroradiologist who will independently assess tumor size and compute percent tumor regression.

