- 12 – Evaluations done within +7 days of off-treatment date unless indicated; do not repeat: if MRI within 14 days of off-treatment date; if H&P /neuro-exam, KPS, labs within minus 5 days of off-treatment date.
- 13 – Adverse Events must be followed for at least 30 days from the last dose of lapatinib, until resolution, within +14 days.

Drug Distribution and Pharmacodynamic Study of Pulsatile Lapatinib in Surgically Accessible EGFR-Amplified Recurrent High-Grade Glioma

ABTC # 1302

NCI # ABTC-1302

PI: [name]

- 14 – After last dose of study drug, prior to surgery
- 15 – 12-lead electrocardiogram (ECG) must be performed within 2 weeks prior to start of treatment, with QTc  $\leq$ 470 msec.
- 16 – LVEF must be monitored every 12 weeks (3 cycles), including pre-Cycle 1, to ensure that LVEF does not decline below the institutional lower limit of normal. See Section [5.2.2](#).
- 17 – Within minus 5 calendar days of starting cycle
- 18 – For Cycle 1 only, perform scan only if patient will start cycle  $>$ 21 days from post-operative scan (patient must have scan within  $\leq$ 21 days of Cycle 1 start). Record glucocorticoid dose at time of MRI.
- 19 – Perform MRI 1-3 days post-operatively. Record glucocorticoid dose at time of MRI

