### 10.1 Off Treatment Criteria

1. Disease Progression: Remove patient from protocol therapy at the time progressive disease is documented. Disease progression is defined as: Progressive neurologic abnormalities not explained by causes unrelated to tumor progression (e.g. anticonvulsant or corticosteroid toxicity, electrolyte abnormalities, hyperglycemia, etc.) or a greater than 25% increase in the measurement of the tumor by MRI scan. If neurologic status deteriorates, on a stable or increasing dose of steroids, or if new lesions appear on serial MRI, further study treatment will be discontinued
2. Adverse Event:
  - Intercurrent illness that prevents further administration of treatment
  - Patients who experience unacceptable toxicity. Patients removed from study for unacceptable adverse events will be followed until resolution or stabilization of the adverse event.
3. Patient Withdrawal: Patient's refusal to continue treatment: in this event, document the reason(s) for withdrawal.
4. Non Compliance: Failure to comply with protocol (as judged by the investigator such as compliance below 80%, failure to maintain appointments, etc.)
5. Physician Decision: If at any time the treating physician feels constraints of this protocol are detrimental to the patient's health remove the patient from protocol therapy.
6. Protocol Defined Delay:
  - Patients who experience a treatment-related toxicity causing a delay in treatment > 14 days
  - Delay in protocol > 28 days for major events or other non-treatment related delays
7. Death

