## 10.2 Off Study Criteria

Patients will only be off study at the time of death. All patients will be followed for survival every 2 months for the first two years from the off treatment date; after 2 years, patients will be followed every 6 months until death. Survival status may be obtained by phone call, clinic visit, or medical records (e.g. physician notes/laboratory results of clinic or hospital visit).

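### PFS in Section 11 item 6 counts progression only if a scan at least 8 weeks later confirms it; the protocol schedules no such scan, so PFS is biased upward if the rule is applied as written

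*Combined protocol and SAP*

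**What the plan says.** Section 11.0, Secondary and Exploratory Objectives item 6, defines progression for PFS as radiographic growth of 25% or more, "increasing from baseline scan with a confirmatory scan at least 8 weeks apart from the initial scan that tumor progression was observed". A confirmed progression is dated back to the first of the two scans. Kaplan-Meier estimates and a binomial 6-month rate are planned; the 6-month definition also requires the patient to be living.

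The rest of the protocol handles progression as follows.

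- Section 8.1 sets the imaging interval: "subjects should be re-evaluated at the end of every 2 cycles (approximately every 8 weeks) with a contrast-enhanced cranial MRI scan". It defines progressive disease by any one of six criteria and asks for no confirming scan. A confirming scan, at 4 weeks, is asked for only for complete and partial response.
- Section 8.2 adds one kind of extra scan: "If during any scheduled MRI, the subject has a Complete Response or Partial Response, the MRI should be repeated prior to the next cycle".
- Section 10.1, on progression: "Remove patient from protocol therapy at the time progressive disease is documented". It also says that "if new lesions appear on serial MRI, further study treatment will be discontinued".
- Section 9.1, footnote 12 in both groups' tables, on the off-treatment visit: "Evaluations done within +7 days of off-treatment date unless indicated; do not repeat: if MRI within 14 days of off-treatment date".
- Section 10.2, on what follows: "All patients will be followed for survival every 2 months for the first two years from the off treatment date". Survival status may come from a telephone call, a visit or records; no imaging is asked for.

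**The concern.** Item 6 makes a second scan a condition for counting a progression, while the rest of the protocol ends scheduled imaging at about the time of the first. A patient can be taken off treatment for progression and still not be a PFS event. Item 6 is also framed differently from the definition used to assess patients in Section 8.1, so some progressions would not qualify even if a late scan existed.

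What is at stake is the reported median PFS and 6-month PFS. Analysts would have to report figures under a rule that the schedule cannot satisfy, or choose another definition once the data are in hand.

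**Working it through.** The documents state no assumed PFS, so there is no planned figure to reproduce. The check compares the item 6 event with the schedule and with Section 8.1.

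**1. Can a scheduled scan confirm a progression?**

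- Confirmation needs at least 8 × 7 = 56 days after the first progression scan (item 6).
- The 8-weekly MRI belongs to treatment cycles, which end when progression is documented (10.1).
- The extra MRI in 8.2 follows complete or partial response, not progression.
- The only MRI left is the off-treatment one, at most 7 days after the off-treatment date (9.1). It could confirm only if that date came at least 56 − 7 = 49 days after the progression scan, which does not fit removal at the time progression is documented. If the progression scan lies within 14 days of the off-treatment date, this MRI is not repeated at all.
- Section 10.2 then collects survival status only.

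Scheduled scans that could confirm, with 10.1 followed: none.

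**2. Do the two definitions cover the same events?**

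| Section 8.1 criterion (any one; no confirmation) | Counterpart in item 6 |
|---|---|
| (a) ≥25% growth over the smallest measurement, with steady or rising steroid dose | ≥25% growth over baseline, confirmed; no steroid condition |
| (b) T2/FLAIR increase | None |
| (c) New lesion | None stated |
| (d) Clinical deterioration | None |
| (e) Not returning because of death or decline | Death only, and only in the 6-month definition |
| (f) Progression of non-measurable disease | None |

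Five of the six have no clear counterpart. For (a), the references differ once a tumor has shrunk. Take a partial response of exactly 50% from a baseline measurement B. Section 8.1 calls progression at 1.25 × 0.5B = 0.625B; item 6 requires 1.25B.

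**3. Which way does this move PFS?**

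A confirmed progression keeps the date of its first scan, so confirmation does not delay events; it removes those that are never confirmed. A removed progression is treated in one of two ways:

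- The patient is censored. Replacing an event by a censoring at the same time cannot lower the Kaplan-Meier curve at any point.
- The patient runs on to a later event such as death. Moving an event later cannot lower the curve either.

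In the 6-month rate, a progressed patient who is alive at 6 months would be scored progression free. Every route leads upward.

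**4. Is there an effect in the other direction?**

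Yes. Growth while the steroid dose is being reduced could count under item 6 but not under 8.1(a). This is probably small, and such growth would still need the unscheduled confirming scan.

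**The case against.** The strongest reply is that PFS is the last of six secondary/exploratory objectives, with no hypothesis, power statement or decision rule. Requiring confirmation is a legitimate guard against pseudoprogression, and sites may scan patients after treatment anyway. Criterion 8.1(d) is left to the treating physician in an open-label trial, so a radiographic-only definition has its own appeal.

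Much of this stands. It limits how serious the point is, and the choice to confirm is not itself the error. But a confirmation rule needs a scan, and the plan neither schedules one after progression nor provides for collecting one done off protocol.

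Three stronger readings are tempting, and the documents do not support them.

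- A reader might infer that the 8-weekly schedule narrowly misses confirmation. MRI is done "Within minus 5 calendar days of starting cycle", so consecutive scans can be 56 − 5 = 51 to 56 + 5 = 61 days apart. That supposes treatment continuing past progression, which 10.1 rules out.
- A reader might infer a biased group comparison, because Group A starts lapatinib on Day −2 and the Reference Group up to 30 days after surgery, apparently 2 + 30 = 32 days apart. Item 6 plans no between-group comparison of PFS. Nor is 32 a true maximum: with the permitted fifth dose, resection can fall 3 days after the first dose, giving 33. The missing time origin and censoring rule are details to supply, not a demonstrated bias.
- A reader might infer that Kaplan-Meier PFS will exceed overall survival. That could happen if unconfirmed progressors were censored, but item 6 states no censoring rule.

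**Conclusion.** The concern holds. Item 6 sets a condition that the trial's own schedule cannot meet and leaves out most of the ways in which Section 8.1 recognises progression. PFS is biased upward if three things are true: item 6 is applied as written, treatment stops at documented progression as 10.1 says, and no off-protocol scans are obtained and collected.

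The size cannot be derived from the documents; any percentage or number of months would rest on assumed progression and survival times. One limit follows from the definition: the binomial 6-month PFS cannot exceed 6-month survival, because the patient must be alive, and it would equal 6-month survival if no progression could be counted. The steroid difference is a probably small offset, so 8.1 should not be described as wider in every respect.

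A reader might extend this to the trial's main conclusions. The documents do not support that: the primary PK and PD rules use tumor concentration and the ratio of phosphorylated to total EGFR, and PFS enters neither. This is a correction that should be made to a secondary endpoint.

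**What to change.** In Section 11 item 6:

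- Define the PFS event as the first progression by any Section 8.1 criterion, or death from any cause, dated at first documentation.
- Remove the 8-week confirmation as a condition for an event. If it is kept, count an unconfirmed progression followed by removal from treatment, clinical decline or death as an event at the first scan.
- While editing, state the time origin and censor patients without an event at the last evaluable MRI.

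The progression wording in 8.1, 10.1 and item 6 must also be reconciled. Section 10.1 is a third version: it uses growth of more than 25% and names no reference scan. This point takes no position on when treatment should stop.

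The core change is to Section 11 wording and uses assessments already scheduled. Its costs are a lower PFS figure, some pseudoprogression counted as events, and reliance on physician judgment for 8.1(d) in an open-label trial. Showing the radiographic-only result alongside would make that last effect visible. Scheduling a scan 8 weeks after progression instead would require changing 9.1 and would still miss patients who die or decline first. Under either definition, patients who leave treatment for toxicity or by withdrawal have no MRI scheduled after the off-treatment one, so their later radiographic progression may go unobserved.
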